## **DATA COLLECTION**

### *Portable Polysomnography*

The Embletta Gold ® is a battery-operated device that can sample data at a 1000 Hz sampling rate and store data at 200 Hz, with 1 GB of storage capacity allowing storage of data from up to 20-24 hrs of recording. The device contains the critical sensors which are recommended by the American Academy of Sleep Medicine as validated sensors for measuring OSA: nasal pressure/flow; thoracic and abdominal inductance plethysmography (effort); and finger pulse oximetry (oxygen saturation).

Relevant PSG Variables: A registered polysomnologist will score the sleep study data. Apneas will be classified as "central" or "obstructive" according to the absence or presence of respiratory effort respectively. Hypopneas will be scored as a 50% amplitude reduction in inductance or flow and associated 3% oxygen desaturation or arousal. Periodic breathing will be defined as airflow or inductance channels increasing and decreasing at least 50% from the maximum, in a cyclic waxing and waning or "sinusoidal" manner for a consecutive period of  $\geq 10$  min.

### *Continuous Overnight 12-lead ECG Monitoring*

CardioDay Holter (GE) monitoring reads SEER 12 data and exports Holter data as individual 10 second, 12 lead reports up to six per minute, i.e. all recorded data. The monitor is capable of continuous 12-lead ECG monitoring with the ability to record up to 10 days with Bluetooth ® technology and 12-bit signal resolution with up to 1024 sampling rate.

ECG Sensor Application. This will be performed by a trained research coordinator at the visit in tandem with sleep monitor lead hook-up. Participants will be asked to remove clothing from the waist up to attach the sensors to the chest. Staff will ensure privacy by covering the participant with a sheet or gown. The staff will shave necessary areas on the chest prior to sensor application to ensure that the sensors stick closely to the skin and will provide the participant with the ECG monitor/holster/clip, leads, communicator and charger, electrodes and a handbook with simple pictorial/written educational instructions. A research coordinator will be available by phone 24-7 to address issues with device malfunction, lead placement and replacement of equipment. ECG quality grade data will be collected: (excellent: >90% of ECG data without artifact, good: 70-90% without artifact, fair: 50-70% without artifact, poor <50% artifact free).

Relevant ECG Variables. Standard average QT interval measures will be obtained with eventual ability to

examine peri-apneic and peri-hypopneic alterations in QT interval. Novel QT morphologic assessments will be made with the GE compatible platform described below.

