## SPECIFIC AIMS

**Aim 1.** To examine the extent that OSA severity and degree of hypoxia are associated with QT interval prolongation and novel T wave morphologic assessments on serial hourly 12-lead ECG collected during overnight polysomnography and also corrected QT interval (QTc) from daytime 12-lead ECG in those predisposed to prolonged QT interval, i.e. those with 1) LQTS, 2) acquired heart disease and 3) arrhythmogenic drugs.

**Hypothesis 1.** We hypothesize that the extent of severity of OSA and degree of hypoxia (defined by the apnea hypopnea index and percentage of sleep time spent <90% respectively) will be associated

with QT interval prolongation and novel T wave morphologic assessments even after consideration of confounding factors including age, sex, race and body mass index. Exploratory analyses will examine the mediation of cardiac substrate (left ventricular ejection fraction) on these associations.

**Aim 2.** To investigate the effect of OSA treatment with 3-month continuous positive airway pressure (CPAP) on QT interval duration as well as novel biomarkers of T wave morphology observed on ECG data collected during overnight polysomnography and also QTc collected from daytime 12-lead ECG in those with LQTS.

**Hypothesis 2.** We postulate that 3-month treatment of OSA will reduce the QT interval and improve novel electrophysiologic markers of ventricular stability in patients who are vulnerable to VTA and sudden cardiac death.

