## **PROTOCOL**

Potential participants will come to the Cleveland Clinic Clinical Research Unit (CRU) for informed consent, eligible participants will undergo a 12 lead electrocardiogram. If the participants is found to have long QT syndrome ( $QT_c \geq 450$  in men and  $\geq 470$  in women) they will continue on in the study. If they are found to not have long QT syndrome they will exit the study. If continuing on in the study the participant will undergo a fasting venipuncture and blood pressure measurements. The participant will then be shown how to use the portable sleep study hook-up and continuous 12-lead ECG monitoring to be monitored in the home setting. The sleep study and ECG monitors will be returned by a courier service the next morning.

Those participants who are identified to have OSA (apnea hypopnea index  $\geq 5$ , estimate 50% of those recruited) on the portable sleep monitoring will be invited to wear CPAP for 2-3 months with a follow up visit with repeat portable polysomnographic and continuous electrophysiologic assessments and CRU visit for bloodwork and blood pressure.

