#### *Novel QT analysis platform*

An analysis system which enables biopharmaceutical companies to analyze detailed morphology of the electrocardiography (ECG) T-wave (QT Guard Plus™, eResearchTechnology, Inc.). The system identifies and quantifies characteristic changes in the shape of the T-wave found in drugs that produce Torsades de Pointes (TdP), the latter a potentially lethal tachyarrhythmia. QT Guard Plus imports individual 10 second, 12 lead reports for analysis and parameter extraction, i.e. T wave shape measures with the capability to extract other electrophysiologic signatures as well.

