**Aim 2. Examine the effect of OSA (AHI $\geq$ 5) treatment for 3 months on QT interval duration.**

For this subgroup of OSA (AHI $\geq$ 5, estimated to be 50% of n=50) and we will perform t-tests to compare pre- and post- treatment mean outcome (Primary outcome: QT duration) and also novel quantitated T wave morphologic measures. For either outcome for which a departure in normality is found (based on the Shapiro-Wilk test) but a transformation of the outcome can not be found to adequately address the issue, we will use the Wilcoxon signed rank sum test to detect a difference in the distribution of the pre- and post- responses. This assessment is not intended to be confirmatory, but rather to provide estimates of variability and effect sizes to inform future studies/randomized trials. Linear regression models will then be developed to QT interval duration at the 3-month visit by conditioning on baseline QT interval duration, baseline OSA, and time from baseline to 3-month visit. Additional adjusted models will carefully consider the covariates list above.

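### No masking, reading order or measurement method is specified for QTc and T-wave readings, so in the uncontrolled pre/post CPAP comparison a reading shift between visits could not be told from a treatment effect

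*Combined protocol and SAP*

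**What the plan says.** All references are to the combined protocol and SAP.

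- **QT.** Under Continuous Overnight 12-lead ECG Monitoring: "Standard average QT interval measures will be obtained". No reader, algorithm or order is given. The Statistical Analytic Plan makes corrected QT the primary outcome.
- **T wave.** Under Novel QT analysis platform: "QT Guard Plus imports individual 10 second, 12 lead reports for analysis and parameter extraction". The operator and settings are not stated. The section adds that the software can extract other electrophysiologic measures, but does not say that QTc will come from it.
- **Segments.** The Holter system "exports Holter data as individual 10 second, 12 lead reports up to six per minute, i.e. all recorded data". Aim 1 under Specific Aims speaks instead of "serial hourly 12-lead ECG collected during overnight polysomnography and also corrected QT interval (QTc) from daytime 12-lead ECG". Aim 2 also names the daytime QTc as an outcome.
- **Quality.** "ECG quality grade data will be collected", in four bands of artifact-free percentage. No grader is named and no use of the grade is described.
- **Scoring.** The only scorer named is for sleep: "A registered polysomnologist will score the sleep study data".
- **Design.** Under Protocol, participants with AHI of at least 5 "will be invited to wear CPAP for 2-3 months". For Aim 2 the SAP states: "we will perform t-tests to compare pre- and post- treatment mean outcome".

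Masking or blinding is not mentioned anywhere.

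**The concern.** QT measurement can depend on choices: which ten-second reports enter the average, what is discarded as artifact, whether a person corrects the automated reading, and which software version and settings are used. If these choices differ systematically between baseline and follow-up, through drift or expectation, the difference appears as a change in QTc. Hypothesis 2 is directional (treatment shortens QT), so expectation has a direction in which to act.

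A randomized control group read in the same way would cancel such a shift. Aim 2 has none. The CPAP intervention section does call subjects randomized, but no comparator or allocation is described anywhere.

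At stake is what Aim 2 is meant to deliver: an effect size on which later trials will be planned. In Aim 1 the exposure is AHI, so the matching risk is that ECGs are selected or read by someone who knows it.

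**Working it through.** **The plan's own figure.** The documents give no reading error and no SD of within-person QTc change, so there is no figure to reproduce on this point. The detectable differences under Power by Aim concern OSA versus no OSA and are not used here.

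**Step 1. What is fixed and what is open.**

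| Item | Fixed in the plan | Left open |
|---|---|---|
| QTc (primary) | an average is taken | reader or algorithm, order, masking |
| T wave | software platform | operator, version, settings, masking |
| Segments | all reports exported; hourly ECGs in Aim 1 | how one becomes the other |
| Quality grade | percentage bands | grader, definition of artifact, use |

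Six reports per minute is 6 × 60 = 360 per hour. If hourly means one ten-second report per hour, a rule is needed to choose 1 of 360. If all are averaged, the choice moves to artifact rejection.

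**Step 2. Where a shift goes.** Let b be a systematic difference in reading, follow-up minus baseline. For each participant:

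observed change = CPAP effect + other time effects + b + random error

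The mean change therefore contains b in full. The Aim 2 regression conditions on baseline QT, baseline OSA and elapsed time. A shift common to all follow-up readings goes into the intercept, and none of these terms separates it from CPAP.

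**Step 3. Size.**

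- n = 25 pairs: 50% of 50 (SAP, Aim 2).
- Two-sided alpha = 0.05 (Power by Aim).
- SD of change = 15, 20 or 25 ms: assumption.
- b = 1, 2, 3 or 5 ms: assumption.
- True CPAP effect and other time effects = 0, so every rejection is false.

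The paired t statistic follows a noncentral t distribution with n − 1 = 24 degrees of freedom and noncentrality b × √n / SD. The critical value is 2.064. Examples:

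- b = 3, SD = 15: 3 × 5 / 15 = 1.00, rejection rate 16.1%.
- b = 3, SD = 25: 3 × 5 / 25 = 0.60, rejection rate 8.9%.
- b = 5, SD = 15: 5 × 5 / 15 = 1.67, rejection rate 36.0%.

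| Shift b | SD 15 ms | SD 20 ms | SD 25 ms |
|---|---|---|---|
| 0 ms | 5.0% | 5.0% | 5.0% |
| 1 ms | 6.2% | 5.7% | 5.4% |
| 2 ms | 9.8% | 7.7% | 6.7% |
| 3 ms | 16.1% | 11.1% | 8.9% |
| 5 ms | 36.0% | 22.5% | 16.1% |

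If 20% drop out, the upper end of the range the group reports from its own studies, n = 25 × 0.80 = 20. A 5 ms shift then gives 13.6% (SD 25) to 29.4% (SD 15). The bias in the mean change is b ms whatever n and SD are.

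No size is computed for Aim 1. It would need an assumed relation between AHI and reading error, for which the documents give no basis.

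**The case against.** The strongest case on the other side is that little room for judgment may remain. T-wave values come from software, all reports are exported, hourly sampling suggests a clock rule, and the quality bands have fixed cut-offs. A fully automated pipeline with unchanged settings would leave little to expectation. This stands as far as it goes, but the plan does not commit to such a pipeline for QTc, and exporting every report does not say which are measured.

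Several stronger readings are tempting, and the documents do not support them:

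- *That ECGs are read unmasked.* The documents are silent. They support only that no masking is specified.
- *That the people processing ECGs know visit and OSA status.* A coordinator attaches the leads, and CPAP usage goes to the research team, but neither is said to process ECGs. AHI cannot be known at the baseline hook-up, because the sleep study follows it. Processing dates are not given either.
- *That the quality grade biases the outcome.* No passage uses the grade to exclude or weight data.
- *That knowing OSA status distorts the pre/post test.* Everyone in that test has OSA. Visit is what matters there, and AHI matters in Aim 1.

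It is also fair that the shifts are assumed, that a 1 ms shift barely moves the error rate, and that the SAP presents Aim 2 as non-confirmatory. The last point makes the false-positive rate secondary. It does not help with bias, because the effect estimate is the intended product.

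**Conclusion.** The concern holds as a gap in specification with a real consequence for Aim 2. The plan does not state who or what measures the primary outcome, in what order, from which segments, or under what masking, and the single-group comparison cannot separate a reading shift from CPAP. A shift of b ms biases the effect size by b ms. Under the stated assumptions the false-positive rate is close to nominal at 1 ms (5-6%) and reaches 16-36% at 5 ms. Whether any shift would occur, and how large, cannot be told from the documents, so this is a sensitivity range and not a prediction. For Aim 1 the risk is qualitative.

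A reader might infer that masking would make the pre/post estimate a valid CPAP effect. It would not: regression to the mean after the QTc entry threshold, and other changes over time, would remain.

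**What to change.** Amend Continuous Overnight 12-lead ECG Monitoring and Novel QT analysis platform as follows.

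1. Name the QT reader or algorithm, and prespecify the segment and artifact rule. Reconcile the hourly ECGs of Aim 1 with the export of all recorded data.
2. Code every research ECG file, overnight and daytime 12-lead, with a random number, so that it carries no visit, date, CPAP or AHI information.
3. Process each participant's baseline and follow-up files in one batch, in random order, with the same software version and settings. Mix in files from participants who have only a baseline night, so that a pair does not reveal OSA.
4. Lock the values before linking them to visit (Aim 2) and AHI (Aim 1).
5. Leave the entry-eligibility reading prompt and unmasked. Re-measure the same daytime tracing in coded form for the outcome.

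The cost is file-coding work by existing staff on stored digital recordings, with no added visits, equipment or participants. The downside is that research QT values for CPAP participants are available only after follow-up.

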#### *Novel QT analysis platform*

An analysis system which enables biopharmaceutical companies to analyze detailed morphology of the electrocardiography (ECG) T-wave (QT Guard Plus™, eResearchTechnology, Inc.). The system identifies and quantifies characteristic changes in the shape of the T-wave found in drugs that produce Torsades de Pointes (TdP), the latter a potentially lethal tachyarrhythmia. QT Guard Plus imports individual 10 second, 12 lead reports for analysis and parameter extraction, i.e. T wave shape measures with the capability to extract other electrophysiologic signatures as well.

#### *Resting Blood Pressure*

BP will be measured after the participant has been sitting quietly for at least 5 minutes following standardized guidelines using a calibrated sphygmomanometer. Cuff size will be determined by measuring the circumference of the upper arm, measured at the midpoint and identifying the appropriate bladder size from a standard chart. Measurements will be repeated three times and recorded.

#### *Fasting Venipuncture*

Phlebotomy (40cc) will be performed the morning of the baseline and follow-up visits using standard techniques by trained research staff following written procedures (e.g., pre-labeled bar coded tubes, minimizing trauma, etc.). The sample will be divided into tubes for the varied analyses (20 mL clot for serum, 20 mL EDTA). Clots will be centrifuged and the serum removed within 1 hr of venipuncture. Plasma from EDTA samples will be stored for future DNA analysis. Assays will be stored in dedicated, alarmed freezers at -80°C in the CRU Core Lab and transferred to designated space in the Pathology and Laboratory Medicine Institute.

Morning blood work to examine the association of electrolytes in relation to QT interval duration and stability upon follow up after use of CPAP. With collateral funding, bloodwork will allow for examination of markers of systemic inflammation which may serve as intermediary pathways for cardiac electrophysiologic biomarkers of VTA in OSA.

#### *Continuous Positive Airway Pressure Intervention*

Subjects randomized to CPAP will be provided with an Autopap REMstar device (Philips-Respironics, Inc, Murrysville, PA) with integrated humidifier, set at a pressure range of 4-20 cm H2O, with auto-titration according to the device's algorithm for detecting airflow limitation which provided wireless transmission of usage information to our research team.

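### The plan calls CPAP randomized, but Aim 2 is an uncontrolled pre-post comparison in people admitted on a high QTc, and the baseline ECG is not fixed

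*Combined protocol and SAP*

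**What the plan says.** The Combined protocol and SAP describes the route to CPAP in several places.

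- **Continuous Positive Airway Pressure Intervention:** "Subjects randomized to CPAP will be provided with an Autopap REMstar device". No comparator, allocation ratio, randomization method or control arm appears here or elsewhere.
- **PROTOCOL:** participants with an apnea hypopnea index (AHI) of at least 5 on the home study "will be invited to wear CPAP for 2-3 months with a follow up visit". No follow-up visit is described for participants without OSA.
- **Analytic Method by Aim, Aim 2:** in the OSA subgroup, "we will perform t-tests to compare pre- and post- treatment mean outcome", with a signed-rank fallback. A regression then models the 3-month QT "by conditioning on baseline QT interval duration, baseline OSA, and time from baseline to 3-month visit". The same paragraph says the assessment is not confirmatory and is meant to yield variability and effect-size estimates for later studies, including randomized trials.
- **POWER BY AIM, Aim 2:** a two-sample t-test of 25 participants with OSA against 25 without.

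On entry, PROTOCOL requires a 12-lead ECG at the consent visit with QTc of at least 450 (men) or 470 (women). Of those below the limit it says: "If they are found to not have long QT syndrome they will exit the study". The STATISTICAL ANALYTIC PLAN makes corrected QT in ms the primary outcome for both aims. SPECIFIC AIMS lists overnight ECG measures and daytime 12-lead QTc as Aim 2 outcomes. No section says which recording supplies the primary value.

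**The concern.** There are two linked problems, and they differ in certainty.

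The first is certain. One section gives the study a property that the rest of the document does not give it. A reader who relies on the intervention section would take the Aim 2 result for a randomized comparison.

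The second is conditional. Participants are admitted because one QTc reading was high. If the same reading is the pre-treatment value, the follow-up mean is expected to be lower even if CPAP does nothing. There is no untreated OSA group to measure that fall. Conditioning on baseline QT in the regression does not replace one, because every participant in the model has been offered CPAP.

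What is at stake is the effect size. Future Directions describes the result as information on the effect size of OSA treatment, and Timeline plans a manuscript on the impact of CPAP on QTc. An estimate inflated by regression to the mean would make the next trial too small.

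**Working it through.** **1. Which design is described?**

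| Section | Who gets CPAP, or what is compared |
|---|---|
| CPAP Intervention | Subjects described as randomized to CPAP |
| PROTOCOL | All with AHI ≥5 are invited |
| Analytic Method, Aim 2 | OSA subgroup, before against after |
| POWER BY AIM, Aim 2 | OSA against no OSA, 25 v 25 |

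PROTOCOL and the Aim 2 analysis agree on a single-arm pre-post design. The other two rows do not fit it. The no-OSA group in the power text is not an untreated OSA control.

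**2. The plan's Aim 2 figure.** The plan states detectable differences of 0.46 SD (80% power) and 0.53 SD (90%). A two-sided 0.05 two-sample t-test with 25 v 25 detects 0.81 and 0.94 SD, so the stated figures do not reproduce. That is a separate defect and adds no weight here. For the paired design actually described, n = 25 detects 0.58 SD of the change at 80% power and 0.68 SD at 90%.

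**3. Expected fall in QTc with no treatment effect, if the qualifying ECG is the baseline.**

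Inputs from the plan: entry limits L = 450 and 470 (ms, as in the outcome definition). Assumed, because the documents give no values: normal QTc among candidates with mean μ = 450 to 480 ms, total SD σ = 30 ms, and within-person SD σw = 10, 15 or 20 ms.

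Formulas:
- a = (L − μ)/σ and λ = φ(a)/[1 − Φ(a)]
- Mean excess of the qualifying reading over μ = σλ
- Expected fall on re-measurement = σλ × σw²/σ²

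The ratio σw²/σ² is 100/900 = 0.111, 225/900 = 0.25 or 400/900 = 0.444.

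Example: L = 450 and μ = 450 give a = 0 and λ = 0.798. The excess is 30 × 0.798 = 23.9 ms. With σw = 15 the fall is 23.9 × 0.25 = 6.0 ms.

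| Limit | μ | Excess (ms) | Fall, σw = 10 | σw = 15 | σw = 20 |
|---|---|---|---|---|---|
| 450 | 450 | 23.9 | 2.7 | 6.0 | 10.6 |
| 450 | 460 | 18.0 | 2.0 | 4.5 | 8.0 |
| 450 | 480 | 8.6 | 1.0 | 2.2 | 3.8 |
| 470 | 450 | 38.0 | 4.2 | 9.5 | 16.9 |
| 470 | 460 | 30.6 | 3.4 | 7.7 | 13.6 |

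Only L − μ matters, so the 470 limit with μ = 480 repeats the 450/460 row (2.0 to 8.0 ms).

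**4. If the overnight recording is the baseline.** Let r1 and r2 be the correlations of the qualifying QTc with the overnight baseline and with the overnight follow-up. With equal SDs, the expected fall is σλ(r1 − r2). It is zero if the two correlations are equal. It is positive if the baseline night, being closer in time, shares transient causes of a high QTc with the qualifying ECG. The bias is therefore reduced but not guaranteed to vanish.

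**The case against.** The strongest reply is that the plan already limits its inference. The Aim 2 paragraph disclaims confirmation and leaves randomized evidence to later trials. Hypothesis 2, "We postulate that 3-month treatment of OSA will reduce the QT interval", is a hypothesis, and a pilot may state a causal one. Both points stand. A reader might infer that the plan commits to a treatment-effect conclusion, but the documents do not support that. The disclaimer does not remove the problem, though, because the effect size it offers instead is the quantity that would be biased.

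The second reply is that regression to the mean is not demonstrated. SPECIFIC AIMS names the overnight ECG first. The data collection section takes average QT from the continuous recording. PROTOCOL lists repeat overnight monitoring at follow-up but no repeat daytime ECG, so the pre-post pair it actually provides for may be the overnight one. This also stands, and it is why the second problem is conditional. Against it, SPECIFIC AIMS includes daytime QTc in Aim 2, and no text stops the qualifying ECG from being the pre-treatment value.

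Third, the size depends on inputs the documents do not give. Recruitment targets people already diagnosed with QT prolongation, so the source mean may be well above the limit and the fall small. The table shows this at μ = 480.

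Finally, a reader might infer from the intervention section that a control arm exists and was left out of the text. Nothing supports this. No ratio, comparator or between-arm analysis depends on the word.

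**Conclusion.** The concern holds in two parts. The randomization wording is contradicted by PROTOCOL and the Aim 2 analysis, and the Aim 2 power statement describes yet another comparison. That part needs no assumption.

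The regression-to-the-mean part holds if the qualifying ECG serves as the Aim 2 baseline, which the plan neither states nor excludes. On assumed total SD 30 ms and within-person SD 10 to 20 ms, the spurious fall is about 1 to 11 ms at the 450 limit (source means 450 to 480 ms) and about 3 to 17 ms at the 470 limit (source means 450 to 460 ms). These ranges are illustrations, not estimates for this population.

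A reader might go further and say that any Aim 2 change will be an artefact, or that a control arm is required. The documents support neither. The bias is conditional, its size is unknown, and a pilot with a declared non-confirmatory purpose can run single-arm if it is described and reported as such. The point should be acted on, but the pilot status keeps it from being critical.

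**What to change.** 1. In the CPAP intervention section, replace the randomization wording with a reference to participants who accept CPAP. State once that Aim 2 is a single-arm pre-post comparison.
2. Bring the Aim 2 power statement into line with that design, as a paired comparison in the OSA subgroup.
3. Name overnight QTc, which does not decide entry, as the primary Aim 2 measure at both baseline and follow-up.
4. Do not use the qualifying ECG as the pre-treatment value. If a daytime comparison is kept with it, label that comparison as subject to regression to the mean.
5. In Future Directions and the planned CPAP manuscript, describe the result as an uncontrolled change from baseline that may still include some regression to the mean and time effects. Hypothesis 2 can stay as written.

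The cost is wording, a revised power statement and the use of a recording already planned. No new arm, visit or participant is needed. The downside is a weaker claim for Aim 2 and a demoted daytime QTc comparison.
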